15/10/2019

ID study number: 08/2019

Cover Page

**Effectiveness of a Psychological Intervention Focused on Expressive Writing in Patients
undergoing to Kidney Transplant**

Background

Kidney transplantation is a replacement therapy in chronic renal failure which could allow a better quality of life. However, renal transplantation also represents an emotionally strong experience, which is associated with feelings of acceptance of the transplanted organ, change in lifestyle, side effects of pharmacotherapies, anxiety, depression, redefinition of one's body, as well as one's own social and family role. For these reasons it can be experienced as a traumatic event and be associated with an unfavorable post-operative course, in particular with regard to adherence to medical prescriptions and the consequent increase in the possibility of rejection. Adherence, in fact, implies the correct management of drugs and the constant and assiduous presence at pre-established check-ups at the transplant center, taking the required exams and promptly reporting any complications. In kidney transplant patients, adherence to immunosuppressive therapies becomes fundamental to reduce the risk of organ rejection or, in the most extreme cases, the risk of death. Several studies show the importance of adherence to post-operative course treatment in different types of transplant (Stilley et al., 2010, Rebafka et al, 2016). Furthermore, it has been shown that poor levels of adherence, recognized as a risk factor for organ rejection, are associated with an increase in healthcare costs (Muduma et al., 2016). Among the risk factors of non-adherence in kidney transplant patients there are young age (Gremigni et al, 2007), depression and anxiety (Reber et al., 2016), avoidant-type adaptation strategies (eg avoiding the stressful event) (Pisanti et al., 2016). Also, alexithymia (known as the inability to identify and describe emotions), the inability to regulate intense emotional states (Calia et al, 2015; Lai et al, 2016), and attachment style (Calia et al, 2015), are associated with poor levels of post-transplant adherence. Possemato and collaborators (2010), showed the efficacy of an intervention focused on expressive writing in the reduction of post-traumatic stress symptoms in kidney transplant patients. This technique seems to be effective also in patients with chronic pathologies (Smyth et al., 1999; McGuire et al., 2005, Norman et al., 2004) and cancer (Gallo et al, 2015), in particular in the reduction of symptoms , in the management of disease and psychophysical symptoms in cancer patients. The ways in which this technique acts are not yet clear, however it is hypothesized that the externalization and processing of traumatic events linked to the disease may favor an improvement in the ability to express emotions, and the reduction of negative thoughts and feelings to it associated (Frattaroli et al, 2006). These studies suggest that using the technique of expressive writing in kidney transplant patients would allow them to externalize and process emotions, feelings and thoughts related to illness, transplantation and consequent

changes (constant controls and therapies, sudden change in the style of life, drug therapies and its effects, physical modifications), and that this can favor a mental reorganization of negative events, a greater expression and regulation of the emotions related to them, and the improvement of the relational style with family members and medical staff. Furthermore, this could be associated with a greater ability to cope with the consequences and psychophysical changes following transplantation and encourage greater levels of adherence with effects on the risk of organ rejection and health costs.

The hypothesis of the present study was that the expressive writing treatment produces an improvement in the emotional condition, levels of adherence and renal function, and a decrease in healthcare spending.

Material and Method

Thirty-five patients were recruited at the kidney transplant center of the Policlinico Umberto I, Sapienza University of Rome. Each participant completed an informed consent form. The sample was divided into two groups in a randomized way. Of the 35 patients, 3 were excluded for not completing the task, due to logistical problems and due to the hospital situation, 1 refused to perform the writing task, and finally 3 dropped to T2 (3rd post-transplant month). Of the remaining 28 recruited patients, 2 had an acute rejection before starting the writing task. The final sample is $n = 26$.

Each participant completed an informed consent form. Adult patients of Italian nationality with a sufficient level of education in order to understand the questionnaires and to execute the writing task were included in the study. Patients with uncompensated psychopathology, already excluded in the pre-transplant psychiatric evaluation, and / or affected by cognitive impairment, were excluded.

The study had 3 phases:

Pre-operative phase (T0)

The time of admission, just before the kidney transplant. In this phase to all participants were asked socio-demographic information and specific characteristics of the pathology in progress (eg. duration of dialysis treatment, date of transplantation, onset of disease). Then, they completed the following self-administered questionnaires: Beck Depression Inventory (BDI) for the evaluation of depression (Beck et al., 1961), State Trait Anxiety Inventory I and II (STAI Y1 - STAI Y2) for the evaluation of trait and state anxiety (Spielberger

et al. , 1983), Toronto Alexythymia Scale 20-item (TAS-20) (Bagby et al., 1994) for assessing the ability to identify and describe one's emotions, Interpersonal Reactivity index (IRI) (Davis et al, 1980) for the evaluation of empathy and the Health Locus of Control (HLC) for the evaluation of the patient's beliefs on his state of health and a questionnaire for the evaluation of healthcare costs, built ad hoc. To assess the level of adherence, each patient answered to the following question: "Have you ever forgotten to take the drugs prescribed by your treatment plan?" with dichotomous answer yes / no. Finally, in order to assess the pre-transplant renal function values, such as Creatinine, CDK-EPI and azotemia, were collected.

Writing Phase (WP)

Five days after the operation, patients belonging to the experimental group, performed the writing task related to their deepest emotions, thoughts and concerns focused on the disease and the transplant itself, for 3 consecutive days, for 20 minutes a day. They did the writing session in a closed, silent room, which guaranteed their privacy. The instructions were according to the standard delivery by Pennebaker, creator of the technique (Pennebaker et al., 1986), translated and adapted for the specific hospital situation already proposed in a study on urological patients by Solano et al, 2007. Instead, the control group performed the neutral writing task, related to the description of an object in their room, without mentioning emotions, but just describing in a neutral way what they saw, for 3 consecutive days, 20 minutes each day.

The *day of discharge Phase (T1)* and *three months follow up (T2)* all participants filled the questionnaire completed before the operation and they had the blood analysis according to the hospital protocol for transplanted patients.

Statistical analysis

Statistical analysis will carry out using the software Statistica Soft 10.0. In order to evaluate the effectiveness of the expressive writing intervention, an analysis of variance with repeated measures (Fisher's F) and planned comparisons between the two randomized groups will be performed on psychological variables, the renal function indices and the health expenditure. The times taken into consideration will be T0, T1, T2 and the differences between T0, T1 and T2 will be respectively evaluated. To test the hypotheses on the dichotomous variable of adherence, Chi Square test will carry out.

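### The only sample named (26) is formed partly by events after randomisation and no as-allocated analysis is planned, so the comparison is by inference one of completers, at risk of bias

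*Combined protocol and SAP*

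**What the plan says.** The combined protocol and SAP gives the patient flow in Material and Method. After the 35 recruited patients it says "The sample was divided into two groups in a randomized way". It then lists the losses. The task non-completers come first: "3 were excluded for not completing the task, due to logistical problems and due to the hospital situation". A refusal and the losses to follow-up come next: "1 refused to perform the writing task, and finally 3 dropped to T2 (3rd post-transplant month". The early rejections come last: "Of the remaining 28 recruited patients, 2 had an acute rejection before starting the writing task". It closes with "The final sample is $n = 26".

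Under Writing Phase (WP), group membership already exists when writing begins: "Five days after the operation, patients belonging to the experimental group, performed the writing task". The control group has a neutral writing task of the same length, so both arms had a task that could be refused or left unfinished. For T1 and T2 the text says "all participants filled the questionnaire completed before the operation" and that "they had the blood analysis according to the hospital protocol for transplanted patients".

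Statistical analysis plans a repeated-measures analysis of variance over T0, T1 and T2, with planned comparisons of the randomised groups, and a Chi-square test for adherence. It names no analysis set and gives no rule for missing values. Arm sizes and losses by arm appear nowhere in the document.

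**The concern.** Randomisation makes the two groups comparable as allocated. It does not protect a comparison of those who went on to finish the task and return at three months. If the analysis is run on the 26, membership depends in part on what happened after allocation, and the estimate describes completers.

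That estimate is biased if those lost differ from completers by different amounts in the two arms, or if the arms lose different shares of patients who differ from completers. Equal counts lost per arm do not rule this out, so reasons by arm are needed as well as numbers.

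The document gives grounds for caution. Its Background treats attendance at check-ups as part of adherence and links poor adherence to depression, anxiety and alexithymia. Adherence and emotional condition are outcomes here, so patients who refuse a task or do not return may differ on what is measured. The two tasks also differ in emotional content, so reasons for loss could differ by arm. Acute rejection bears on renal function and cost, which are outcomes too.

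**Working it through.** **1. Reproduce the flow** (all counts from Material and Method).
35 − 3 − 1 − 3 = 28, as stated. 28 − 2 = 26, as stated. Left out: 35 − 26 = 9.

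**2. Share left out, by time of allocation** (not stated).
- All 35 allocated: 9/35 = 25.7%.
- The 2 rejections before allocation: 35 − 2 = 33; 7/33 = 21.2%.
- The 4 non-writers also before allocation: 35 − 2 − 3 − 1 = 29; 3/29 = 10.3%. This is strained, because groups existed when writing began, and failing or refusing a task suggests it had been assigned.

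On all three readings the 3 patients lost at T2 left after allocation.

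**3. Possible error in the between-arm difference (illustration only).** The document gives neither arm sizes nor outcome differences. Assume arms of 17 and 18 (14 and 15 for the 29-patient reading), and a gap g of 0.5 to 1 SD between lost patients and completers. With m lost of n in each arm:
- same gap in both arms: error = |mA/nA − mB/nB| × g
- opposite gaps: error = (mA/nA + mB/nB) × g

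Example, 4/3 split of 7 losses, g = 1: 4/17 − 3/18 = 0.069 (same gap) and 4/17 + 3/18 = 0.402 (opposite gaps). Each range below runs over both values of g and both assignments of the arm sizes.

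| Losses counted | Split | Same gap, SD | Opposite gaps, SD |
|---|---|---|---|
| 4: refuser and T2 losses | 2/2 | 0.003–0.007 | 0.11–0.23 |
| 4 | 3/1 | 0.05–0.12 | 0.11–0.23 |
| 7: all except the rejections | 4/3 | 0.02–0.07 | 0.20–0.40 |
| 7 | 5/2 | 0.08–0.18 | 0.20–0.41 |
| 7 | 6/1 | 0.14–0.30 | 0.20–0.41 |
| 7 | 7/0 | 0.19–0.41 | one arm only |
| 9: all | 5/4 | 0.02–0.07 | 0.26–0.52 |
| 3: T2 losses only (arms 14, 15) | 2/1 | 0.03–0.08 | 0.10–0.21 |

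The error is zero if loss is unrelated to outcome in both arms.

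**4. Adherence (illustration only).** Assume 50% answering yes in each arm among those kept, arms of 17 and 18, and all 9 answers missing. Filling these with extreme values moves the arm difference by ±0.5 × (mA/17 + mB/18). That is from ±0.25 (all 9 in the arm of 18) to ±0.265 (all 9 in the arm of 17).

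**5. Precision at T2.** At most 35 − 3 = 32 patients could have T2 values. √(32/26) = 1.11, so the standard error would be up to 1 − √(26/32) = 10% smaller. If 33 were allocated, the most is 30 and the gain 1 − √(26/30) = 7%. If 29 were allocated, the most is 26 and there is no gain.

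**The case against.** The strongest reply is that the text is thinner than the headline count suggests. A reader might infer that 9 of 35 randomised patients were dropped. That rests on sentence order in a paragraph that is not chronological: it lists the month-3 losses before the rejections that preceded writing, and it calls the remaining 28 recruited, not randomised. Groups existing when writing began fits 33 allocated as well as 35. This stands, and it is why the share is given as a range.

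A reader might also infer that the plan prescribes an analysis of the 26. No sentence does. The statement that all participants filled the questionnaires at T1 and T2 rules out only the 3 lost at T2; non-writers and patients with rejection could have answered. A classical repeated-measures analysis of variance likewise needs values at all three times, but does not by itself remove non-writers. The inference rests mainly on 26 being called the final sample, with no other set offered.

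Nor are the losses alike. The 3 task non-completers have logistical and hospital reasons, which may be unrelated to outcome, although the hospital situation could reflect clinical state. The 2 rejections preceded any writing, so neither task caused them. The refuser and the 3 T2 losses alone are 4/35 = 11.4%. The larger errors need uneven splits or opposite gaps, which the document does not show. Same-gap 4/3 and 5/2 splits give 0.02–0.18 SD, against a standard error of about √(1/13 + 1/13) = 0.39 SD for assumed arms of 13 at one time point. All of this limits the size that can be claimed. It does not supply the missing analysis set, missing-value rule or account of losses by arm.

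**Conclusion.** The concern holds as a gap in the analysis plan with a real risk of bias. The only named sample is formed partly by events after allocation on every timing considered, and nothing in the plan provides an as-allocated comparison. Between 10.3% (strained reading) and 25.7% of allocated patients are left out; 21.2% to 25.7% covers the two more plausible readings.

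That the result would be a completers comparison is an inference, though a reasonable one. It would be tempting to conclude that the comparison is biased, or biased in favour of expressive writing. The document supports neither: no losses by arm, no baseline comparison and no outcome gaps are given, and the arm of the refuser is unknown. The SD figures depend wholly on assumed arm sizes and gaps. Near-even losses with the same gap matter little; uneven losses or opposite gaps could matter. Precision is a lesser issue, with a gain of at most about 10% in the standard error at T2, depending on what data exist.

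**What to change.** 1. State when allocation took place, and report losses by arm and reason.
2. Make the primary analysis as allocated, using every available T0, T1 and T2 value from all patients who had been randomised. Include the 2 early rejections if they had been allocated. For continuous outcomes one option is a mixed model, with its missing-at-random assumption stated.
3. For adherence, compare patients by arm allocated, give the denominator at each time, state how missing answers are handled, and show best-case and worst-case values for them.
4. Use T1 and T2 renal values from routine hospital blood results wherever they exist.
5. Keep the 26 completers as a sensitivity analysis.

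The analysis is written in the future tense, so on its face it can still be changed. The cost is plan wording, a flow table by arm and reason, a search of routine blood results, and one model per continuous outcome. The downsides are that the estimate may be diluted by patients who did not write, the T2 questionnaires of the 3 dropouts cannot be recovered, and bias remains possible if loss depends on unobserved outcomes.

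### The adherence item has no recall window: read literally, change from T0 can show only worsening or no change, and a T2 arm difference may be diluted

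*Combined protocol and SAP*

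**What the plan says.** The adherence item is described under the pre-operative phase (T0): "Have you ever forgotten to take the drugs prescribed by your treatment plan", answered yes or no. No reference period is given. For the discharge visit (T1) and the three-month visit (T2), the document says that "all participants filled the questionnaire completed before the operation". It mentions no rewording, and it does not say explicitly that the adherence question belongs to that questionnaire.

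The hypothesis at the end of the Background is that expressive writing "produces an improvement in the emotional condition, levels of adherence and renal function, and a decrease in healthcare spending". The Background also explains why adherence matters here: "adherence to immunosuppressive therapies becomes fundamental to reduce the risk of organ rejection".

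Under Statistical analysis, repeated-measures ANOVA and "planned comparisons between the two randomized groups will be performed on psychological variables, the renal function indices and the health expenditure". A sentence listing T0, T1, T2 and their differences follows. Adherence then has one sentence of its own: "To test the hypotheses on the dichotomous variable of adherence, Chi Square test will carry out".

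**The concern.** A question about whether something has ever happened is a one-way switch. Once a patient has truthfully said 'yes', every later truthful answer is 'yes'. If the item is repeated in the same words, forgetting before the transplant is carried into the T1 and T2 answers, although the behaviour of interest is drug-taking after it.

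This has two consequences. A flat or rising share of 'yes' between T0 and T2 could be misread as lack of benefit, when the item could not have shown a fall. And patients who had forgotten before T0 answer 'yes' at T2 whichever arm they are in, so they cannot contribute to an arm difference even if the writing task helped them. With a final sample of 26, there is little power to spare.

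A separate small-sample point bears on the same analysis. An uncorrected chi-square on two small groups does not always hold its nominal 5% level.

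**Working it through.** **Inputs from the document.** The item wording and yes/no scale (T0 section); the repeat at T1 and T2 (section on those visits); the chi-square (Statistical analysis); and the patient flow (Material and Method): 35 - 3 - 1 - 3 = 28, then 28 - 2 = 26, which agrees with the text. The document gives no adherence rate, significance level, arm sizes or sample-size calculation, so there is no design figure to reproduce.

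**Assumptions, for illustration only.** 13 patients per arm, two-sided 5%, b = 0.4 answering 'yes' at T0, and the forgetting rates shown. Power is by exact enumeration unless stated.

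**Step 1: change from T0.** Let p be the probability of forgetting after transplant among those who said 'no' at T0. Under the literal reading, the recorded 'yes' rate at T2 is b + (1-b)p. This is never below b, so neither arm can show a fall.

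**Step 2: arm difference at T2.** Let d_no and d_yes be the true arm differences among T0 'no' and T0 'yes' patients.
- 'Ever' item: recorded difference = (1-b) × d_no.
- Fixed-window item: recorded difference = (1-b) × d_no + b × d_yes.

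If d_yes = d_no, the 'ever' item records (1-b) times the true difference. If d_yes = 0, the two items record the same difference.

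**Step 3: power of the uncorrected chi-square when T0 forgetters benefit equally, b = 0.4.**

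| True rates, control v writing | Recorded by 'ever' item | Difference, true → recorded | Power, no dilution | Power, 'ever' item |
|---|---|---|---|---|
| 60% v 10% | 76% v 46% | 50 → 30 points | 84% | 41% |
| 50% v 10% | 70% v 46% | 40 → 24 points | 66% | 29% |
| 30% v 10% | 58% v 46% | 20 → 12 points | 23% | 13% |

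For example, 0.4 + 0.6 × 0.60 = 0.76 and 0.4 + 0.6 × 0.10 = 0.46.

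At 60% v 10%, power for b = 0, 0.2, 0.4 and 0.6 is 84%, 63%, 41% and 21%.

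**Step 4: dependence on benefit among T0 forgetters.** Take 60% v 10% in T0 'no' patients and b = 0.4. The 'ever' item always records 0.6 × 50 = 30 points (41% power). A fixed-window item would record:
- full benefit: 30 + 0.4 × 50 = 50 points, power 84%;
- half benefit: 30 + 0.4 × 25 = 40 points, power 63%;
- no benefit: 30 + 0 = 30 points, power 41%, so no loss.

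**Step 5: size of the test.** At 13 v 13 the uncorrected chi-square has exact size 5.0% when the common rate is 25%, 7.0% at 40% and 7.6% at 50%, its maximum. Boschloo's test is at most 4.9%. Boschloo power at 60% v 10% is 81% without dilution and 33% at b = 0.4.

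**Step 6: stratifying by T0 answer.** Mantel-Haenszel without continuity correction, b = 0.4:

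| True rates | Reading | Stratified | Plain chi-square |
|---|---|---|---|
| 60% v 10% | literal | 56% | 41% |
| 60% v 10% | current plan | 80% | 84% |
| 30% v 10% | literal | 12% | 13% |
| 30% v 10% | current plan | 22% | 23% |

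**The case against.** The strongest reply is that the plan never promises an adherence analysis of change from T0. The hypothesis is about what the treatment produces, and the natural use of a chi-square on a binary answer is arm by answer, a contrast that survives the literal reading. This stands. A reader might infer that the item defeats the stated hypothesis or cannot detect any effect, and the document supports neither.

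A reader might also treat the unnamed visit and contrast as a defect peculiar to adherence. That goes too far. The sentence listing T0, T1 and T2 can be read as covering the whole section, and it picks no visit for the other outcomes either. Taken alone, this is missing detail.

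The size of the loss is assumed throughout, and it may be zero. Patients may take the treatment plan to mean the current one, and the Italian wording they saw is not given. For a modest effect such as 30% v 10%, sample size is the main limit with or without dilution.

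Finally, it is tempting to call the T2 comparison in the 26 a clean randomised contrast. The route from 35 to 26 includes refusal of the writing task, non-completion, loss by T2 and rejection before writing. At least some of these appear to follow allocation, so the description needs qualifying.

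What remains is that the item has no window, that its literal reading blocks one comparison and may weaken another, and that the remedy is cheap.

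**Conclusion.** The point holds as a minor one. If the item is repeated unchanged and answered literally and consistently, within-arm change from T0 can show only worsening or no change. This follows from logic and needs no assumed rates.

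The dilution at T2 is conditional. It requires that some patients had forgotten before T0 and that the writing task would benefit some of them. With equal benefit the recorded difference is (1-b) of the true one. With no benefit in that group, or under the current-plan reading, there is no loss. The fall in power from 84% to 41%, or from 23% to 13%, illustrates the mechanism at assumed rates and is not an estimate for this trial.

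The chi-square's excess size, up to 7.6% at 13 v 13, is a separate matter that does not depend on how patients read the item. It does depend on the assumed split and on the common rate.

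**What to change.** 1. Confirm that the adherence question was asked at T2, and report the Italian wording. If it was not asked after T0, no effect on adherence can be tested.
2. For any answers still to be collected, give the T2 item a fixed post-discharge window, for example 'Since discharge, have you forgotten to take any prescribed drug?'. Do not pool answers to the two wordings. This may come too late, because Material and Method already reports the final sample.
3. Make the single primary adherence analysis the between-arm comparison at T2 in all randomised patients with a T2 answer. T1 is the day of discharge, so only T2 covers drug-taking afterwards. State, per arm, the number randomised and the number excluded after allocation. Name Boschloo's test as the deciding p-value, with the chi-square as supportive. The cost in nominal power at 60% v 10% is 81% against 84% without dilution, and 33% against 41% at b = 0.4.
4. Do not describe within-arm change from T0 as improvement or as lack of it.
5. As a secondary analysis, stratify the T2 comparison by T0 answer (Mantel-Haenszel). At b = 0.4 and 60% v 10% it gains 15 points of power under the literal reading (56 - 41) and loses 4 under the current-plan reading (84 - 80). At 30% v 10% it gains nothing.
6. Label every one of these choices post hoc if results by arm have already been seen.

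Apart from any rewording, the cost is a few sentences in the analysis section and a per-arm count of exclusions.

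### Renal indices are analysed over T0, T1 and T2 although T0 predates the graft, which can cost an index with a wide T0 spread, such as creatinine, much of its power

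*Combined protocol and SAP*

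**What the plan says.** The Background section introduces the setting: "Kidney transplantation is a replacement therapy in chronic renal failure". Under Pre-operative phase (T0), the first assessment is at "The time of admission, just before the kidney transplant". History items taken then include "eg. duration of dialysis treatment, date of transplantation, onset of disease". The renal bloods are described with the words "in order to assess the pre-transplant renal function values, such as Creatinine, CDK-EPI and azotemia, were collected" (I read the second index as CKD-EPI).

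At discharge (T1) and three months (T2), participants repeated the questionnaires and "they had the blood analysis according to the hospital protocol for transplanted patients". Writing started five days after surgery. No renal value from between the operation and the first writing session is described.

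The hypothesis is that "the expressive writing treatment produces an improvement in the emotional condition, levels of adherence and renal function", along with lower healthcare spending. The Statistical analysis section names a repeated-measures ANOVA and says that "planned comparisons between the two randomized groups will be performed on psychological variables, the renal function indices and the health expenditure". It continues: "The times taken into consideration will be T0, T1, T2 and the differences between T0, T1 and T2 will be respectively evaluated". It does not say which between-arm comparisons are planned. It states no separate renal model, no adjustment for T0 and no sphericity correction.

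**The concern.** For a questionnaire, T0 measures the same construct in the same person as T1 and T2, so it is a sensible reference. For the renal indices it is not. A different organ is being measured, and the T0 value may also reflect dialysis. Subtracting it, or pooling it into the error term of the interaction, brings in variation that says little about graft function.

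Where the T0 spread is wide and its correlation with T2 is weak, two things follow. The T0-based contrasts lose power, and unequal variances across times break sphericity, so the uncorrected omnibus F rejects too often under the null. Renal function is a named hypothesis and only 26 patients are analysed, so a flat creatinine result could be read as no effect on the graft when the analysis had little chance of showing one.

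**Working it through.** **The plan's own figure.** The only number to reproduce is the final sample: 35 − 3 − 1 − 3 = 28, and 28 − 2 = 26. This agrees. The plan gives no power calculation.

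**Inputs.** Total of 26: Material and Method. Everything else is assumed because the documents are silent: 13 per arm, two-sided 5%, normal data, T1–T2 correlation 0.5, T0 correlation r = 0.1 with later values, and a true arm difference of 1 T2-SD at both T1 and T2. Three creatinine-like SD patterns (T0/T1/T2, mg/dL) were used: A 3/1/0.5, B 2/1/0.5, C 1.5/1/0.7.

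**Formulas.** With s0 and s2 the SDs at T0 and T2:
- SD of the T0–T2 change = √(s0² + s2² − 2·r·s0·s2)
- Noncentrality = (difference/SD) × √(13/2), where √(13/2) = 2.55, on 24 df
- 95% CI half-width = 2.064 × SD × √(2/13)
- Variance ratio, change against T2 adjusted for T0 = (s0² + s2² − 2·r·s0·s2) / (s2²(1 − r²))

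**Change score.**
- A: SD = √(9 + 0.25 − 0.30) = 2.99; noncentrality 0.5/2.99 × 2.55 = 0.43; variance ratio 8.95/0.2475 = 36.2
- B: SD = √(4 + 0.25 − 0.20) = 2.01; noncentrality 0.5/2.01 × 2.55 = 0.63; variance ratio 4.05/0.2475 = 16.4
- C: SD = √(2.25 + 0.49 − 0.21) = 1.59; noncentrality 0.7/1.59 × 2.55 = 1.12; variance ratio 2.53/0.4851 = 5.2

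Arms compared at T2 have noncentrality 2.55 in all three.

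**Results** (40,000 simulated trials per pattern; CI half-widths from the formula):

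| | A | B | C |
|---|---|---|---|
| Power, T0–T2 change | 7% | 9% | 19% |
| Power, group-by-time F, uncorrected | 11% | 13% | 22% |
| Power, group-by-time F, Greenhouse-Geisser | 7% | 9% | 18% |
| Power, arms at T2 | 69% | 69% | 69% |
| Power, T2 adjusted for T0 | 67% | 67% | 67% |
| CI half-width, change (mg/dL) | 2.4 | 1.6 | 1.3 |
| CI half-width, T2 (mg/dL) | 0.40 | 0.40 | 0.57 |
| Null rejection, uncorrected F | 7.7% | 7.2% | 6.6% |
| Null rejection, Greenhouse-Geisser | 4.9% | 5.0% | 4.9% |

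The correction restores the error rate but not the power. The T1–T2 difference avoids T0. Its power is 5% if the effect is equal at both times, and 29%, 29% and 49% if the effect appears only at T2.

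**Dependence on the SD ratio.** The change has a smaller variance than T2 alone only if s0/s2 < 2r, that is below 0.2 at r = 0.1 and below 0.6 at r = 0.3. Change power by ratio, against 69% for arms at T2:

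| s0/s2 | 0.5 | 1 | 1.5 | 2 | 3 |
|---|---|---|---|---|---|
| r = 0.1 | 63% | 44% | 30% | 21% | 12% |
| r = 0.3 | 71% | 54% | 36% | 24% | 14% |

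**CKD-EPI-like index** (T0 SD 2–5, T1 SD 15–20, T2 SD 15, r 0.1–0.3): change power 67–73% against 69% at T2; F power 57–76%, lowest when the T1 SD is 20; null rejection 5.0–5.3%.

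**Second set of assumptions** (20,000 trials per scenario):
- Creatinine, fixed difference 0.5 mg/dL, T2 SD 0.45, T1 SD 0.8, T0 SD 1.5–3.0, r 0–0.3: 78% at T2; 7–14% for the change; 9–17% for the uncorrected F.
- Azotemia, difference 20 mg/dL, T2 SD 18, T1 SD 25, r = 0.1: 77–78% at T2; change power 48% at T0 SD 20, falling to 16% at T0 SD 50.
- CKD-EPI, difference 20, T1 and T2 SD 18, T0 SD 2–5: 77–78% for both T2 and the change.

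**The case against.** The strongest reply is that the plan does mention planned comparisons between the arms on the renal indices, and arms compared at T2 is a natural reading. With that time point's own error term, the T2 power loss would disappear. This stands as a possibility. But the contrasts are not listed, whereas the between-time differences are, so a reader cannot tell whether the efficient comparison was intended or chosen afterwards.

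Second, the loss is not common to all renal indices. That stands: CKD-EPI, if compressed near its floor at T0, loses little or nothing on the change score, and azotemia depends on its T0 spread. The point is limited to indices with a wide T0 spread.

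Third, the size rests on assumed SDs, correlations, arm sizes and effect. That also stands, and the documents cannot place any index on the ratio table. Yet equal SDs with r = 0.1 already reduce 69% to 44%.

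Fourth, a 1-SD renal effect from three 20-minute sessions is generous. At 13 per arm, T2-only power is 50% for 0.8 SD, 23% for 0.5 SD and 11% for 0.3 SD. For moderate effects the sample size is the main limit, and the fix does not make the renal test adequate. It only stops the T0 values from weakening it further.

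Fifth, an effect that emerges after discharge would be seen better by the T1–T2 difference, but its 29–49% is still below the 69% for arms at T2.

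**Conclusion.** The concern holds. The documents themselves establish that T0 is pre-transplant, that T1 and T2 are post-transplant, and that all three enter the renal analysis with no stated exception.

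The size is conditional on the assumptions listed. For a creatinine-like index, the spelled-out T0-based analyses would probably miss a 1-SD graft difference that a T2 comparison would detect about two times in three. The uncorrected omnibus F also runs at roughly 7–8% instead of 5%; the single-contrast change comparison stays at its nominal level. For a CKD-EPI-like index the loss on the change score is negligible. Because the arms are randomised and T0 precedes the writing, this is a loss of precision and not a bias. Confidence in the size is medium, since every SD and correlation is assumed.

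**What to change.** For creatinine, CKD-EPI and azotemia, take T0 out of the repeated factor and do not use it as the reference for change. List the renal comparisons: arms at T2 as the main one and arms at T1, each with T0 as a covariate. A renal value from after surgery but before the first writing session could serve as covariate instead, if one is already on record. Applying one rule to all three indices costs CKD-EPI almost nothing: its T2 comparison adjusted for T0 keeps 67–71% power in the scenarios above. Apply Greenhouse-Geisser wherever the three-time ANOVA is kept.

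The cost is a few lines of SAP text and a re-run of three analyses on T1 and T2 values already collected, with no new patients or visits. Material and Method already reports the final sample, so if the renal data have been seen, the changed analysis must be labelled post hoc and reported beside the one currently described.
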